If bone marrow myeloblasts between 5% and 25% and a decrease from baseline of at least 50% in the marrow myeloblasts, no detectable (or trace of residual) blasts, and no evidence of extramedullary leukemia, the response is classified as PR.

Not Evaluable (NE)/No Response (NR):

In the situation where no bone marrow assessments are performed or myeloblast value is missing, blast value from peripheral blood is missing or $\leq 2\%$, and extramedullary leukemia is missing or not done, the response will be classified as NE. In any case response cannot be categorized as CR, CRp, CRi, PR or NE, it will be categorized as NR.

Relapse:

Relapse after CR, CRh, CRp or CRi is defined as a reappearance of leukemic blasts in the peripheral blood ($>2\%$) or $\geq 5\%$ myeloblasts in the bone marrow not attributable to any other cause or reappearance or new appearance of extramedullary leukemia.

Relapse after PR is similarly defined with reappearance of significant numbers of peripheral blasts and an increase in the percentage of myeloblasts in the bone marrow to $> 25\%$ or $>2\%$ blast in peripheral blood not attributable to any other cause or reappearance or new appearance of extramedullary leukemia.

Best Response:

Best response is defined as the best measured response to treatment for all visits (in the order of CR, CRp, CRi, PR, NR and NE) post-baseline. Subjects who achieve the best responses of CR, CRp, CRi, or PR will be classified as responders. Subjects who do not achieve at least PR will be classified as non-responders.

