6.1.3 Secondary Efficacy Endpoints

[Phase 1 part]

Not applicable.

[Phase 2 part]

- Overall survival (OS)

OS is defined as the time from start date of the first treatment until the date of death due to any cause. For a subject who is not known to have died by the end of long-term follow-up, OS is censored at the date of last known alive.

As a sensitivity analysis, OS is defined similarly as the above, however, subjects who undergo HSCT will be censored at the time of HSCT.

- Event free survival (EFS)

The time from the date of start date of the first treatment until the date of documented relapse after CR, treatment failure or death from any cause, whichever occurs first. For a subject with none of these events, EFS is censored at the date of last disease assessment. Subject without post-treatment disease assessment will be censored at the start date of the treatment.

Treatment failure includes those subjects who failed to achieve CRc by the end of consolidation period, or who discontinued the treatment due to “lack of efficacy” without a previous response.

Treatment failure date refers to the end of treatment date for subjects with treatment failure.

- Relapse free survival (RFS)

The time from the date of achievement of first CRc until relapse or death from any cause, whichever comes first for subjects who achieve CRc. For a subject who is not known to have relapsed or died, RFS is censored on the date of last relapse-free disease assessment date.

Last relapse-free disease assessment date refers to the subject’s last disease assessment date.

- CR rate after each treatment therapy

Defined as the number of subjects who achieve the best response of CR divided by the number of subjects in the analysis population after each treatment therapy period.

Subjects with unknown or missing response, or who provide no information on response will be treated as non-responders and will be included in the denominator when calculating rates.

- CR rate without MRD after each treatment therapy

Defined similarly as CR rate after each treatment therapy. Responders achieve that the best response is CR and MRD status is negative. CRc rate without MRD after each treatment therapy will also be defined similarly.

- CRh rate after each treatment therapy

Defined similarly as CR rate after each treatment therapy.

- CRc (Composite CR) rate after each treatment therapy

CRc: CR + CRp + CRi

Defined similarly as CR rate after each treatment therapy.

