- CR/CRh rate after each treatment therapy

CR/CRh: CR or CRh.

Defined similarly as CR rate after each treatment therapy.

- Duration of CR, CR/CRh, CRh, CRc, response

Duration of CR is defined as the time from the date of achieving first CR until the date of first documented relapse for subjects who achieve CR. Subjects who die without report of

relapse are considered non-events and censored at their last relapse-free disease assessment date. Subjects who come off the study for HSCT will be considered non-events and censored at the time of HSCT. Other subjects who do not relapse on study are considered non-events and censored at the last relapse-free assessment date. Duration of CRh, Duration of CR/CRh, Duration of CRc and Duration of response are defined similarly as Duration of CR.

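### EFS counts relapse only after CR but sets treatment failure at CRc, so a relapse after a CRp- or CRi-only response reached by the end of consolidation is no EFS event unless death follows

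*SAP*

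**What the plan says.** All of this is in the SAP, Phase 2 part.

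- **EFS events (6.1.3).** EFS runs from the start of first treatment "until the date of documented relapse after CR, treatment failure or death from any cause, whichever occurs first".
- **Treatment failure (6.1.3).** "Treatment failure includes those subjects who failed to achieve CRc by the end of consolidation period". A second limb covers stopping treatment for lack of efficacy, but only in subjects with no earlier response. CRc is defined in the same section as CR, CRp and CRi combined.
- **Date of failure (6.1.3).** "Treatment failure date refers to the end of treatment date for subjects with treatment failure".
- **EFS censoring (6.1.3).** "For a subject with none of these events, EFS is censored at the date of last disease assessment". Unlike RFS, the rule is not limited to relapse-free assessments.
- **Responders (6.1.1).** "Subjects who achieve the best responses of CR, CRp, CRi, or PR will be classified as responders".
- **Relapse in general (6.1.1).** "Relapse after CR, CRh, CRp or CRi is defined as a reappearance of leukemic blasts", so the general definition covers loss of CRp and CRi.
- **RFS (6.1.3).** "The time from the date of achievement of first CRc until relapse or death from any cause".
- **Analysis (7.4).** EFS is analysed in the TTE-FAS and summarised descriptively by Kaplan-Meier with 95% confidence intervals. No test or benchmark is attached to it.

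**The concern.** The two disease components of EFS use different response levels. CRp or CRi is enough to escape treatment failure, yet losing that CRp or CRi does not count as relapse. Relapses in this group therefore drop out of EFS, or enter it only later as deaths, while RFS counts them on the day they occur. The clinical study report could list the same subject as relapsed for RFS and event-free for EFS. Because the study has a single arm, there is no comparator in which the effect could cancel.

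**Working it through.** **1. Which subjects fall in the gap.** Each pattern is run through the EFS and RFS rules of 6.1.3.

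| Course | EFS event | RFS event at relapse |
|---|---|---|
| CR reached, then relapse | Relapse | Yes |
| CRp/CRi by end of consolidation, never CR, relapse, alive | None; censored at last disease assessment | Yes |
| Same, then death | Death, dated at death | Yes |
| First CRp/CRi only after consolidation | Treatment failure (deadline missed) | Yes |
| PR only, or no response | Treatment failure | Not in RFS |

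The second and third rows are the gap. Limb 1 of treatment failure is not met because CRc was achieved in time. Limb 2 is not met because 6.1.1 classes CRp and CRi as responses. The relapse is not one after CR. Only death remains. Duration of CRc also counts this relapse, unless the subject left for transplant first: "Subjects who come off the study for HSCT will be considered non-events and censored at the time of HSCT".

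**2. Illustrative size.** The SAP states no EFS figure to reproduce, and no CRp/CRi share, relapse rate or death rate. Only n = 80 and the 70% CR design alternative come from the document (4.1.2). The rest is assumed:

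- share q with CRp/CRi as best response, reached by the end of consolidation: 5%, 10%, 20%;
- relapse rate lr: 0.30 or 0.35 per year;
- death without relapse ld: 0.08 per year;
- death after relapse mu: 0.8 or 1.0 per year.

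The mean overstatement of EFS at time t is q × P, where P is the probability of being relapsed and alive:

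P = lr / (mu − lr − ld) × [exp(−(lr + ld)t) − exp(−mu·t)]

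At t = 2:

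- lr 0.30, mu 1.0: 0.30/0.62 × (0.468 − 0.135) = 0.161
- lr 0.35, mu 1.0: 0.35/0.57 × (0.423 − 0.135) = 0.177
- lr 0.30, mu 0.8: 0.30/0.42 × (0.468 − 0.202) = 0.190
- lr 0.35, mu 0.8: 0.35/0.37 × (0.423 − 0.202) = 0.209

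| Share q | Overstatement at 2 years (points) | Subjects of 80 |
|---|---|---|
| 5% | 0.8 to 1.0 | 0.6 to 0.8 |
| 10% | 1.6 to 2.1 | 1.3 to 1.7 |
| 20% | 3.2 to 4.2 | 2.6 to 3.4 |

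With CR at 70% and non-responders counted as early failures, 2-year EFS under a CRc rule is (0.70 + q) × exp(−2(lr + ld)); the as-written value adds q × P. For q = 5%, lr 0.30, mu 1.0 this gives 35.1% against 35.9%. For q = 20%, lr 0.35, mu 0.8 it gives 38.1% against 42.3%.

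**3. Against sampling error.** The half-width is 1.96 × √[p(1 − p)/80]: 10.3 points at p = 0.328 and 10.9 at p = 0.453. The shift is well inside it.

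**4. Direction in the Kaplan-Meier estimate.** Each affected subject's event moves later or disappears. The estimate need not follow, because an event moved past censored subjects carries more weight. Take 10 subjects, one relapsing at 0.5 years and dying at 1.5, with five others censored at 1.0. Dated at relapse, the estimate is 1 − 1/10 = 0.90. Dated at death, with five still at risk, it is 1 − 1/5 = 0.80.

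**The case against.** **CR may be shorthand for any complete remission.** This does not stand. CR, CRp, CRi and CRc are separately defined, and CRc is used for treatment failure within the same EFS definition and again for RFS. A programmer following the text would code CR only.

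**Not every CRp/CRi responder is affected.** A reader might infer that anyone whose best response is CRp or CRi is exposed. The text does not support that. Best response is taken over all visits, while treatment failure has a deadline at the end of consolidation, so a first CRp or CRi after that is already an EFS failure. Subjects who reach CR before relapsing are also covered. This objection stands and sets the scope of the point.

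**The wording need not lengthen the reported EFS.** A reader might infer that it can only do so. That holds for each subject's event time, not for every Kaplan-Meier estimate, as the 0.90 against 0.80 example shows. With the rates above and an assumed drop-out of 15% per year, simulated trials of 80 subjects gave a lower 2-year estimate as written in roughly a quarter of data sets at a 5% share, and in fewer than one in ten at 20%. The mean shift stayed upward. With no censoring before 2 years the as-written estimate was never lower.

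**The effect is small and the inputs are assumed.** This stands. The 4.2-point upper end needs a 20% share on top of 70% CR, that is 90% CRc. At a 5% share the effect is under one subject. RFS reports these relapses in any case.

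**A CR-only relapse rule may be deliberate, or taken from the protocol.** The SAP alone cannot exclude this. A deliberate CR-only EFS would, however, be expected to define failure on CR too, and the SAP does not.

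**Conclusion.** The inconsistency is established from the SAP's own text and does not depend on any assumed rate. It is confined to subjects who reach CRp or CRi by the end of consolidation, never reach CR and then relapse. Their EFS event is delayed to death or lost, never brought forward, and EFS is biased upward on average.

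The size cannot be known from the SAP. Under the assumed rates it is about 0.8 to 4.2 points at 2 years, less than sampling error. A reader might infer that the main efficacy conclusion is at risk. It is not: the primary endpoint is the CR rate after induction, the sample size rests on that rate alone, and EFS is secondary, descriptive and untested. Severity is minor, but the text should be corrected because it makes two reported secondary endpoints disagree about the same event.

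**What to change.** Use one response level in both EFS components and state it.

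- **Preferred.** Make the relapse component *documented relapse after CRc (CR, CRp or CRi)*. This matches RFS and the existing treatment-failure limb. It costs one phrase in 6.1.3 and one condition in the derivation program. EFS becomes slightly less favourable on average, by the 0.8 to 4.2 points above under the assumed inputs.
- **If a CR-only EFS is intended.** Define treatment failure on CR as well and say so. This is a materially different endpoint: every CRp/CRi-only subject becomes a failure dated at end of treatment. The fall in 2-year EFS from the as-written value is at most q × [exp(−2(lr + ld)) + P], with the bracket between 0.600 and 0.658. That is about 3.0 to 3.3 points at a 5% share, 6.0 to 6.6 at 10% and 12.0 to 13.2 at 20%. These limits apply if all such subjects have ended treatment by 2 years; the fall is smaller if some are still in maintenance.

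If the protocol carries the same EFS wording, record either change as a change from the protocol, as 7.6.2 and 7.7.1 already do for PK and PD.

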5.1 Full Analysis Set (FAS)

[Phase 1 part]

Subjects who meet all of the following criteria will be included:

- Received at least 1 dose of study drug
- Assessed for at least 1 efficacy variable after study drug administration

[Phase 2 part]

Subjects who meet all of the following criteria will be included:

- Received at least 1 dose of study drug
- Had at least one post-baseline bone marrow assessment

For the statistical analysis of some Time-to-Event efficacy variables, TTE-FAS will be used. TTE-FAS is defined similarly as the FAS, however, the criterion for bone marrow assessment is removed.

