7.4 Analysis of Efficacy

[Phase 1 part]

The efficacy analysis will be performed on the FAS.

For response variables, best response after each treatment therapy period will be summarized. The number and percentage of subjects in each category will be presented together with two-sided exact 95% CIs based on binomial distribution. Swimmer's plot will be presented for response variables.

For time-to-event variables efficacy analysis will be summarized using descriptive statistics. The survival curve and the median will be estimated using the Kaplan-Meier method and will be reported along with the corresponding 95% CIs.

[Phase 2 part]

The efficacy analysis will be performed on the FAS and TTE-FAS. The interpretation of statistical results will be based on the FAS. The TTE-FAS will be used to analyze OS and EFS. Analysis of MRD and MR will be performed using MAS.

Primary efficacy variable

For primary efficacy variable, CR rate after induction therapy period, the two-sided 90% exact CI by Clopper-Pearson method will be calculated. The lower limit will be used to compare with the benchmark of CR rate of 55%. The number and percentage of subjects in each category and swimmer's plot will also be presented. As a supportive analysis, CR rate after induction therapy period reported by Day 60 and CR rate after induction therapy period not being dependent on RBC and platelet transfusion (No Transfusion of RBC and Platelet within 1 week prior to disease assessment) will also be calculated.

Other efficacy variables

For other efficacy variables, analysis method will be described as follows:

Categorical variables:

The number and percentage of subjects in each category will be presented together with two-sided exact 95% CIs based on binomial distribution. Swimmer's plot will be presented for response variables.

For response assessment variables, best response rate after each treatment therapy will be summarized. The number and percentage of subjects in each category will be presented together with two-sided exact 95% CIs based on binomial distribution. For subjects who undergo HSCT, any response assessment data after HSCT will not be used (i.e. for those subjects, only response assessment data before HSCT will be used).

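### SAP 6.1.3: the rule censoring unassessed subjects for EFS at Day 1 is not limited to event-free subjects and has no precedence against death or treatment failure

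*SAP*

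**What the plan says.** All the EFS rules for the Phase 2 part are in SAP section 6.1.3.

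- **Events.** EFS runs from the start of first treatment "until the date of documented relapse after CR, treatment failure or death from any cause, whichever occurs first".
- **General censoring.** "For a subject with none of these events, EFS is censored at the date of last disease assessment".
- **No assessment.** The next sentence reads: "Subject without post-treatment disease assessment will be censored at the start date of the treatment".
- **Treatment failure.** "Treatment failure includes those subjects who failed to achieve CRc by the end of consolidation period". A second limb adds subjects who discontinued for lack of efficacy with no earlier response.
- **Date of failure.** "Treatment failure date refers to the end of treatment date for subjects with treatment failure".

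Section 7.4 fixes the analysis set: "The TTE-FAS will be used to analyze OS and EFS". Section 5.1 describes that set: "TTE-FAS is defined similarly as the FAS, however, the criterion for bone marrow assessment is removed".

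**The concern.** The general censoring sentence carries its own condition, that no event has occurred. The sentence on unassessed subjects does not repeat it, and nothing in the section says which rule wins when a subject has an event but no assessment. Treatment failure is dated at end of treatment, so it can be assigned without any disease assessment. A subject can therefore fit both the event wording and the Day 1 censoring wording.

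The subjects concerned are those who die or stop treatment before the first assessment, so their events come early. A subject censored at time zero adds nothing to a Kaplan-Meier curve. Moving such a subject from event to Day 1 censoring can only raise the estimate. Two statisticians could also produce different EFS curves from the same data, each able to point to a sentence in 6.1.3.

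**Working it through.** **The plan's own figure.** The SAP states no event count, rate or power for EFS, so there is no EFS figure to reproduce. Its one Phase 2 design figure is the power of the CR-rate test in section 4.1.2 (70 subjects, 55% against 70%, one-sided 0.05). An exact binomial calculation requires at least 46 CRs and gives alpha 0.0452 and power 0.820, which agrees with the stated more than 80%. This has no bearing on EFS.

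**How the sentences apply.** Consider three subjects, none with a disease assessment after starting treatment.

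| Subject | Event definition | Day 1 sentence, literal | Day 1 sentence, event-free subjects only |
|---|---|---|---|
| Dies on Day 20 | Event (death) | Censored at Day 1 | Event at death |
| Stops on Day 15 for toxicity, no CRc | Event at end of treatment if the first failure limb covers early stops; otherwise none | Censored at Day 1 | Depends on the scope of the first limb, which the SAP does not settle |
| No death, no failure | None | Censored at Day 1 | Censored at Day 1 |

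Only the third row is free of difficulty. Day 1 censoring is acceptable there.

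**Size of the effect.** Inputs: N = 80, the planned Phase 2 enrolment in section 4.1.2. The number k of displaced events and the level of EFS are not in the SAP and are assumed. All k events occur before time t, and nobody else is censored before t.

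Let EFS(t) be the estimate with the k subjects censored at Day 1. It is then the estimate in the other 80 − k subjects. Counting the k as events gives EFS(t) × (80 − k)/80, so the overstatement is EFS(t) × k/80.

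| EFS(t), k censored at Day 1 | k = 2 | k = 4 | k = 8 |
|---|---|---|---|
| 50% | 48.75% (1.25 points too high) | 47.5% (2.5) | 45.0% (5.0) |
| 70% | 68.25% (1.75) | 66.5% (3.5) | 63.0% (7.0) |

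Over EFS(t) from 40% to 70% and k from 1 to 10, the overstatement runs from 0.40 × 1/80 = 0.5 points to 0.70 × 10/80 = 8.75 points.

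The same effect from the other side: with 20 events among 80 by 6 months, all counted, EFS is 60/80 = 75.0%. If k of those 20 are censored at Day 1, it becomes 60/(80 − k): 60/78 = 76.9%, 60/76 = 78.9% and 60/74 = 81.1% for k = 2, 4 and 6.

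On the median, assume an exponential curve with a median of 12 months in the other subjects. Counting the k as early events moves it to −12 × log2(0.5 × 80/(80 − k)), that is 11.6, 11.1 and 10.2 months for k = 2, 4 and 8.

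**The case against.** The strongest reply is that the sentence should be read in sequence. It follows directly on the rule for subjects without an event and supplies a censoring date when there is no last assessment to use. On that reading an early death stays an event. This largely stands: it is the more natural reading, so a reader who infers that the SAP expressly removes early deaths from EFS goes too far. Deaths are exposed by loose wording and missing precedence, not by a stated rule.

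The second reply concerns treatment failure. If every early stop without CRc met the first limb, the separate limb for lack of efficacy would add little. One can therefore read the first limb as covering subjects followed to the end of consolidation and the second as covering early stops for lack of efficacy only. A toxicity stop is then not a failure and nothing conflicts. This reading is available, but the SAP does not adopt it. If it is meant, unassessed early stops leave EFS with zero follow-up, and the plan should say so.

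A reader might also infer that the TTE-FAS was created for exactly these subjects and that the Day 1 rule makes it pointless for EFS. The documents do not support that. The FAS criterion which the TTE-FAS drops is "Had at least one post-baseline bone marrow assessment", whereas the EFS sentence speaks of a disease assessment, which the SAP does not define as marrow only. Section 6.1.1 also draws on peripheral blasts and extramedullary disease. The TTE-FAS serves OS too, where these subjects contribute, and on the event-free reading it also brings their deaths into EFS.

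Finally, the sizes are hypothetical, since the SAP supplies neither k nor an expected EFS, and on the event-free reading the deaths among the k add no bias. Both points stand.

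**Conclusion.** The concern holds as a fault of precedence and scope. Taken literally, the Day 1 sentence contradicts the event definition for subjects who die or fail before any assessment. Taken more naturally, it leaves open whether an unassessed early stop without CRc is an event at end of treatment or is censored at time zero. The text does not settle that question, so neither answer can be called the SAP's rule.

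The direction is certain: any displaced event raises EFS. The size is not known. It is EFS(t) × k/80 on the assumptions that N is 80, that the displaced events fall before t and that there is no other earlier censoring; 2.5 points at k = 4 and 50% is an illustration only.

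EFS is a secondary endpoint, reported in section 7.4 by Kaplan-Meier with 95% confidence intervals and with no test or benchmark. The primary CR conclusion does not depend on it. The change is worth making because it costs little and removes a possible upward bias.

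**What to change.** Make three changes in section 6.1.3.

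1. Reword the sentence along these lines: *An event-free subject who has no disease assessment after starting treatment is censored on the day treatment began; death and treatment failure take precedence over this rule.*
2. State whether ending treatment before CRc for a reason other than lack of efficacy counts as treatment failure. Apply the answer alike to assessed and unassessed subjects. Making only the unassessed stops failures would go beyond the present text and could treat similar subjects differently.
3. Add a sensitivity analysis that counts every unassessed subject who ended treatment without CRc as an event at the end of treatment date.

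The cost is a few sentences in the SAP and one extra Kaplan-Meier run. The EFS estimate may become slightly less favourable. Sample size, data collection and the primary analysis do not change.

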6.5 Other Variables

- FLT3-ITD mutation status
- FLT3-TKD mutation status
- FLT3 mutation status

Either of FLT3-ITD mutation status or FLT3-TKD mutation status is positive, this variable shows positive.

- MRD

MRD negative is defined as summed FLT3-ITD signal ratio of any post-baseline sample $\leq 10^{-4}$. MRD positive is defined as summed FLT3-ITD signal ratio of any post-baseline sample $> 10^{-4}$.

- MR
MR is defined as summed FLT3-ITD signal ratio of any post-baseline sample $\leq 10^{-2}$.
No MR is defined as summed FLT3-ITD signal ratio of any post-baseline sample $> 10^{-2}$.
- FLT3-ITD signal ratio
FLT3-ITD signal ratio is defined as the ratio of FLT3-ITD sequence reads divided by the total number of FLT3 sequence reads. This is being calculated by central laboratory. For subjects with more than one FLT3-ITD variant, the FLT3-ITD signal ratio will be summed at each timepoint.
- Duration of exposure (days)
Duration of exposure to each treatment will be calculated in days, using the following formula:
 - Duration of exposure for each treatment cycle is defined as Last dose date – First dose date + 1 – (on-study HSCT period for subjects undergo on-study HSCT) for each cycle. For Phase1 part, last dose date of study drug exposure = (initial dose date of the cycle + 14 – 1) if last dose date of the cycle is not captured on dosing CRF.
 - Duration of exposure for each treatment period is calculated as sum of the duration of exposure for each treatment cycle.
 - Duration of exposure during study for study drug =
(Duration of exposure for Induction period) + (Duration of exposure for Consolidation period) + (Duration of exposure for Maintenance period).When the last date of exposure is beyond cutoff date, the cutoff date will be used as the last date of exposure. When the start or stop date is missing, then the exposure will be treated as missing.
- Number of dosing days (days)
Defined as number of days with non-zero dosing.
Number of dosing days is calculated for each treatment period.
- Cumulative dose (mg or g)
Defined as total amount of drug given to a patient, which calculated as follows:
 - ASP2215: Sum of (actual dose level * number of dosing days within each dose level)
 - Chemotherapy: Sum of actual dose across the days when administered.
Actual dose is calculated as:
(Actual volume administered / Total volume prepared)* Intended dose * Body surface area.

If number of doses taken is unknown, it will be treated as missing.

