7.11.5 Visit Windows

[Phase 1 part]

Visit windows are allowed for certain visits per the schedule of assessments. Subject data will not be excluded from analyses due to the subject’s failure to comply with the visit schedule. In the case of multiple observations at a specific visit, the observation which is closest to the target date will be used. If the observations have the same distance to the target visit, the latest one will be used. The baseline visit is the last measurement taken prior to initial treatment.

- Visit Windows for Laboratory Tests

Induction period			
Assessment timing	Scheduled date (Day 1: Day 1 of each cycle Start of treatment)	Acceptable time range	Remarks
Screening	—	7 days before dosing – 1 day before dosing (Before dosing if the screening and Day 1 of Cycle 1 overlap).	Treatment on Day 1 may be started on the day informed consent is obtained when the investigator or subinvestigator judges that immediate treatment is required due to rapid proliferative disease progression. In this case, among the test items specified in both screening and Day 1 of Cycle 1 are not required to be performed twice.
Day 1	Day 1	Before dosing on the scheduled date	Same as above
Day 4	Day 4	Scheduled date	
Day 8	Day 8	Scheduled date	
Day 15	Day 15	Scheduled date ± 1 day	
Day 28	Day 28	Scheduled date ± 7 days	
Day 42	Day 42	Scheduled date + 14 days	
Consolidation period			
Assessment timing	Scheduled date (Day 1: Day 1 of each cycle Start of treatment)	Acceptable time range	Remarks
Day 1	Day 1	Scheduled date	
Day 4	Day 4	Scheduled date	
Day 8	Day 8	Scheduled date	
Day 15	Day 15	Scheduled date – 1 day	
Day 28	Day 28	Scheduled date ± 7 days	
Maintenance period			
Assessment timing	Scheduled date (Day 1: Cycle 1 Day 1 Start of treatment)	Acceptable time range	Remarks
Cycle 1 Day 1	Day 1	Scheduled date	
Cycle X Day 1	Day 28 (X – 1) + 1	Scheduled date ± 3 days	X = Cycle 2 and subsequent cycles

End of treatment (for any period) or at the end of Cycle 26 of the maintenance period	Date of judgment of discontinuation or Cycle 26 Day 28 of the maintenance period	Scheduled date + 7 days	If the scheduled tests at discontinuation have been performed after the final study drug administration, the tests do not have to be repeated even if they were performed before the date of judgment of discontinuation.
---	--	----------------------------	---

● Visit Windows for Vital Signs

Induction period			

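### EFS: failure to reach CRc is settled by the end of consolidation but dated at the end of treatment, so a failing subject who stays on treatment has the event recorded late, or has no event date at the cutoff

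*SAP*

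**What the plan says.** SAP section 6.1.3 measures EFS from the start of first treatment "until the date of documented relapse after CR, treatment failure or death from any cause, whichever occurs first".

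Treatment failure has two limbs:

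- Limb 1: "Treatment failure includes those subjects who failed to achieve CRc by the end of consolidation period".
- Limb 2: "or who discontinued the treatment due to" lack of efficacy, with no previous response.

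One sentence dates both limbs: "Treatment failure date refers to the end of treatment date for subjects with treatment failure".

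The censoring rule covers only subjects without an event: "For a subject with none of these events, EFS is censored at the date of last disease assessment".

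Treatment can run beyond consolidation. Section 6.5 defines study-drug exposure as the sum "Duration of exposure for Induction period) + (Duration of exposure for Consolidation period) + (Duration of exposure for Maintenance period". The Phase 2 visit table in section 7.11.5 runs to Day 1 of maintenance Cycle 26, placed 700 days after maintenance Cycle 1 Day 1.

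**The concern.** Limb 1 is tied to a deadline. A subject who has "failed to achieve CRc by the end of consolidation period" is a failure from that point, whatever happens to dosing afterwards. The dating sentence moves the event to the day treatment stops. The two dates part company whenever a limb 1 subject is still being treated after consolidation.

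This has two consequences:

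- Two subjects who both miss the deadline can get different EFS times only because one was treated for longer.
- A limb 1 subject still on treatment at the data cutoff has met the failure criterion but has no end-of-treatment date. The censoring sentence does not clearly apply either, because it is written for subjects with none of the events. The programmer would have to invent a rule.

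The trial is single-arm and uncontrolled, so no concurrent group shares the dating rule. Any distortion goes straight into the reported EFS curve and median.

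**Working it through.** **Is there a plan figure to reproduce?** Not for EFS: the SAP gives no EFS event count, power or sample size. Its only power figure (section 4.1.2) is for the CR rate: 70 subjects, 55% against 70%, one-sided 0.05, more than 80% power. The exact binomial rule rejects at 46 or more CRs of 70, with exact alpha 0.045 and power 0.820, so the figure reproduces. EFS dating does not enter it.

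**Can another rule stop the clock earlier?** A subject who never remits cannot relapse after CR. Before treatment ends, only death can end that subject's EFS. The sensitivity analyses named in the SAP concern OS censored at HSCT (6.1.3), response data after HSCT (7.4) and an optional look at COVID-19 (7.1). None varies the failure date.

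**Longest lag for one subject.** Inputs are the Phase 2 visit table in 7.11.5 and 28-day cycles.

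- Cycle 26 Day 1 = maintenance Day 1 + 25 × 28 = + 700 days, as tabulated.
- Cycle 26 Day 28 = 700 + 27 = + 727 days.

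Any gap between the end of consolidation and maintenance Day 1 adds to this. The shortest lag is zero, when treatment stops by the end of consolidation.

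**Effect on the curve (illustration).** These assumptions are not in the SAP: consolidation ends at day 180; a share *f* of subjects are limb 1 failures; none of them dies; the other subjects have exponential EFS with a median of 730 days; a share *g* of the failures continue on treatment for at least 364 days past consolidation.

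- Other subjects at day 365: exp(−ln 2 × 365/730) = 0.707.
- Failure dated at the end of consolidation: EFS(365) = (1 − *f*) × 0.707.
- Failure dated as in the SAP: EFS(365) = (1 − *f*) × 0.707 + *f* × *g*.

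The overstatement at 12 months is therefore *f* × *g*.

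| Failures *f* | End of consolidation | SAP rule, *g* = 25% | SAP rule, *g* = 100% |
|---|---|---|---|
| 10% | 0.636 | 0.661 | 0.736 |
| 20% | 0.566 | 0.616 | 0.766 |
| 30% | 0.495 | 0.570 | 0.795 |

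At *f* = 20%, the overstatement is 0.20 × 0.25 = 5 points, or 0.20 × 1 = 20 points if every failure continues.

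**Median at *f* = 20%.** Dated at the end of consolidation, the median is 495 days. Under the SAP rule, with continuation lasting 364 to 727 days, it is 544 to 606 days if a quarter continue and 544 to 907 days if all do.

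**Short continuation.** If failures stay on treatment only 84 days past consolidation, to day 180 + 84 = 264, then both 12-month EFS (0.566) and the median (495 days) are unchanged. Only the stretch of curve from day 180 to day 264 is raised.

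**The case against.** The strongest objection is that the size rests on a protocol not shown here. The SAP does not say whether a subject without CRc may go on to maintenance. Section 7.2.2 shows that withdrawal criteria exist. If they take such subjects off treatment by the end of consolidation, the two dates nearly coincide and the shift is close to nil. This stands, and it makes the size uncertain. It does not make the sentence right: a limb defined by a deadline should not be dated by another event.

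Several stronger readings are tempting, but the SAP does not support them:

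- *A never-remitting subject is event-free for as long as dosing continues.* Death from any cause ends EFS at any time, and limb 2 is sensibly dated at the end of treatment. The fault is confined to limb 1.
- *A subject found refractory at the induction marrow is dated late.* Under the SAP's definition that subject is not yet a failure and may still reach CRc in consolidation. The reading brings in a different definition of EFS.
- *The bias always runs one way.* The SAP does not define the end-of-treatment date. If it means the last dose, it could precede the assessment that shows failure. Lateness follows only for limb 1 subjects treated beyond consolidation.
- *A failure still on treatment at the cutoff is carried as event-free.* The SAP does not say so; it leaves the case without a rule.
- *The overstatement is 20 points.* That is a ceiling. It needs every failure to be alive and on treatment at the landmark.

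It is also fair to say that the consequence is limited. Section 7.4 reports EFS by a Kaplan-Meier curve and median in the TTE-FAS, with no hypothesis test.

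**Conclusion.** Wrong as written, for limb 1 only. The sentence dates the event later than the deadline that defines it whenever a subject without CRc stays on treatment after consolidation. It gives no date at all when that subject is still on treatment at the cutoff.

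The lag per subject runs from none to about 727 days, plus any gap before maintenance, and death cuts it short. On the stated assumptions with 20% failures, the overstatement of 12-month EFS is nil if no failure continues, about 5 points if a quarter continue for 364 days or more, and at most 20 points. Neither the share of failures nor the share continuing is given in the SAP, so these figures show scale and are not forecasts.

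The point touches a descriptive secondary endpoint. The primary CR-rate analysis, its power and the sample size do not change.

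**What to change.** Replace the dating sentence in section 6.1.3 with text that separates the limbs:

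> For subjects who fail to achieve CRc by the end of the consolidation period, the treatment failure date is the earlier of the end-of-treatment date and the end of the consolidation period; this applies also to subjects still on treatment at the data cutoff. For subjects who discontinue due to lack of efficacy without a previous response, it is the end-of-treatment date.

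This does not backdate failure to an induction marrow, and it leaves limb 2 as it is. The cutoff clause is meant for subjects who have passed the end of consolidation. The SAP should also say which recorded dates count as the end of consolidation and the end of treatment.

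Keep the current dating as a sensitivity analysis, with a stated rule for failures still on treatment at the cutoff.

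The cost is a short change of text and one derivation, with no new data. EFS estimates may become slightly less favourable; on the illustration above the drop would be larger if many failures continue. The change concerns only how the event is dated and says nothing about who should stay on treatment.
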